10.2.4 Other safety topics of interest

Other safety topics of interest for this study include:

- Infections (serious, opportunistic, fungal and tuberculosis)
- Malignancies
- Major adverse cardiac events (MACE)
- Neutropenia
- Suicidal Ideation and Behavior (SIB)
- Inflammatory bowel disease
- Hypersensitivity (including Anaphylaxis)
- Hepatic events and drug-induced liver injury (DILI)

The analyses produced for the other safety topics of interest are based on the specifications described in the BKZ safety topic of interest document version from Apr-2021.

The incidence of other safety topics of interest will be summarized by MedDRA SOC, HLT, and PT. The EAIR with associated 95% CI and the EAER will be included in the summary tables.

Output tables will be produced for categories of other safety topics of interest as described below separately for the DBP in the SS, the ATP on the ATS and on the combined DBP and ATP in the AMS.

10.2.4.1 Infections (serious, opportunistic, fungal and TB)

Serious infections will be identified based on MedDRA classification (SOC “Infections and infestations”) using the “Any SAE” table. A separate table does not need to be produced to summarize these events:

- Fungal infections will be summarized in a stand-alone table. The table will include all TEAEs (serious and non-serious) which code into the High-Level Group Term (HLGT) “Fungal infectious disorders”.
- Opportunistic infections (including tuberculosis) will be summarized in a stand-alone table. The table will include all opportunistic infection TEAEs identified using UCB-defined search criteria. The process for identifying opportunistic infections is outlined in a separate document located in Appendix 2.

10.2.4.2 Malignancies

Two tables will be produced for malignancies:

- A table will be based on the criteria SMQ= “Malignant or unspecified tumours (SMQ)”.
- A table will be based on the criteria SMQ= “ Malignant tumours (SMQ)”.

SMQ search should include all TEAEs which code to a PT included in the Scope=Narrow group within each SMQ.

Note that the events included in the “Malignancies” table will be a subset of the events included in the “Malignancies (including unspecified)” table. While the “Malignant tumours (SMQ)” is most relevant, “Malignant or unspecified tumours (SMQ)” must be reviewed for potential malignancies.

The output tables will include 2 different overall incidence rows:

- The first overall incidence row will summarize “Any Malignancy” and this row will summarize the incidence of all AEs flagged for inclusion in the table (using the appropriate SMQ depending on the table), regardless of the High Level Term (HLT) it codes to.
- The second overall incidence row will summarize “Any Malignancy excluding non melanotic skin cancers HLT” and this row will summarize the incidence of AEs flagged for inclusion in the table (using the appropriate SMQ depending on the table), excluding those which code to an HLT of “skin neoplasms malignant and unspecified (excl melanoma)”.

10.2.4.3 Major adverse cardiac events (MACE)

The classification of an event as MACE is determined by an external cardiovascular event adjudication committee.

- Major adverse cardiac events will be presented in a table.
- Extended MACE events will be presented in a separate table and listing. All events which are classified by the adjudication committee as any of the following event types will be considered an extended MACE event.

Table 10-1: Type of Extended MACE events

Event Type Code	Event Type
1	Non-Fatal Myocardial Infarction (MI)
2	Non-Fatal Stroke: hemorrhagic
3	Non-Fatal Stroke: ischemic
4	Non-Fatal Stroke: embolic
5	Non-Fatal Stroke: undeterminable
6	Hospitalization or ER for Unstable Angina with urgent revascularization
8	Hospitalization for Heart Failure

Event Type Code	Event Type
10	Coronary Revascularization Procedures (eg percutaneous coronary intervention, coronary artery bypass grafting)
11	Urgent Revascularization Procedures (ie due to symptoms of brain ischemia or pending infarction)
18	Death due to Myocardial Infarction (MI)
19	Death due to Stroke
20	Sudden Cardiac Death
21	Other CV Death (eg heart failure, pulmonary embolism, cardiovascular procedure-related)
22	Cardiovascular: Undetermined Cause of Death (ie cause of death unknown)

- A separate table and listing will present the adjudicated cardiovascular events by type. For each cardiovascular event type (24 in total, for the full list of adjudicated cardiovascular events refer to the Bimekizumab-Event-Adjudication-Committee-Analysis-Plan), the individual PTs which fall within each event type will be summarized.
- Additionally, a listing of all events identified for potential review by the cardiovascular event adjudication committee will be produced. This listing will indicate whether each event was escalated to the committee for formal review/adjudication.

10.2.4.4 Neutropenia

A table will be created based on the following PTs (regardless of seriousness):

- Autoimmune neutropenia
- Band neutrophil count decreased
- Cyclic neutropenia
- Febrile neutropenia
- Idiopathic neutropenia
- Neutropenia
- Neutropenic infection
- Neutropenic sepsis
- Neutrophil count decreased

10.2.4.5 Suicidal Ideation and Behavior Neuropsychiatric events

An external neuropsychiatric adjudication committee will evaluate potential neuropsychiatric events and determine whether any of those events were associated with suicidal ideation and

behavior (SIB). If an event is adjudicated as SIB, further information will be provided. A table and listing for SIB events as determined by the adjudication committee will be produced.

A separate table will present the adjudicated neuropsychiatric events by type. For each neuropsychiatric event type (6 total), the individual PTs which fall within each event type will be summarized. It will include events adjudicated as SIB and events adjudicated as non-suicidal. Note that the event type Suicidal ideation can be classified as either SIB or non-suicidal.

Additionally, a listing of all events identified for potential review by the neuropsychiatric adjudication committee will be produced. This listing will indicate whether each event was escalated to the committee for formal review/adjudication. A separate listing will also be produced to summarize the adjudicated results of all events escalated to the full committee.

10.2.4.6 Inflammatory bowel disease

An external inflammatory bowel disease (IBD) adjudication committee will evaluate potential IBD events and will classify each one as follows:

- Event Type Code 1: Possible IBD – Crohn’s Disease
- Event Type Code 2: Probable IBD – Crohn’s Disease
- Event Type Code 3: Definite IBD – Crohn’s Disease
- Event Type Code 4: Possible IBD – Ulcerative Colitis
- Event Type Code 5: Probable IBD – Ulcerative Colitis
- Event Type Code 6: Definite IBD – Ulcerative Colitis
- Event Type Code 7: Possible IBD – Unclassified
- Event Type Code 8: Probable IBD – Unclassified
- Event Type Code 9: Definite IBD – Unclassified
- Event Type Code 10: Symptoms not consistent with IBD
- Event Type Code 11: Possible Inflammatory Bowel Disease – Microscopic Colitis
- Event Type Code 12: Probable Inflammatory Bowel Disease – Microscopic Colitis
- Event Type Code 13: Definite Inflammatory Bowel Disease – Microscopic Colitis
- Event Type Code 14: Possible Inflammatory Bowel Disease – no further differentiation possible
- Event Type Code 15: Probable Inflammatory Bowel Disease – no further differentiation possible
- Event Type Code 16: Definite Inflammatory Bowel Disease – no further differentiation possible

- Event Type Code 99: Not enough information to adjudicate

A table for adjudicated IBD events (event type codes 1, 2, 3, 4, 5, 6, 7, 8, 9, 11, 12, 13, 14, 15 and 16) as determined by the adjudication committee will be produced. It will summarize events determined by the adjudication committee as definite IBD (event type codes 3, 6, 9, 13, and 16), probable IBD (event type codes 2, 5, 8, 12, and 15) and possible IBD (event type codes 1, 4, 7, 11, and 14). Definite and probable IBD will also be aggregated and summarized. This table will be stratified by subjects with or without a previous medical history of IBD. Previous medical history of IBD will be determined using the information recorded on the Extra-Articular Assessment at Screening CRF page ("Does subject have a history of IBD?").

A separate table will present the adjudicated gastrointestinal events by type. For each gastrointestinal event type (17 total), the individual PTs which fall within each event type will be summarized. It will include events determined by the adjudication committee as definite IBD probable IBD and possible IBD. It will also include events determined as Symptoms not consistent with IBD (event type code 10) and Not enough information to adjudicated (event type code 99).

A listing of all events identified for potential review by the IBD adjudication committee will be produced. This listing will indicate whether each event was escalated to the committee for formal review/adjudication.

A listing will present the adjudicated IBD events by type. For each IBD event type (event type codes 1 through 16 and 99; 17 total), the individual PTs which fall within each event type will be listed.

A third listing will present the individual diagnostic criteria met for each adjudicated IBD event.

10.2.4.7 Hypersensitivity (including Anaphylaxis)

A table will be prepared based on the MedDRA anaphylaxis Algorithm (see Appendix 1) for acute anaphylactic events (reported on the same day as when an injection was administered or one day after). An AE glossary table will also be produced to summarize the MedDRA coding for these events. The glossary table will include the following fields: reported term, PT, LLT, HLT, and SOC.

A table will be prepared to summarize hypersensitivity events, identified using the SMQ "Hypersensitivity (SMQ)". All TEAEs which code to a PT included in the Scope=Narrow search will be included in this table. In addition, a separate table will be prepared to summarize serious hypersensitivity events, identified using the SMQ "Hypersensitivity (SMQ)". All serious TEAEs which code to a PT included in the Scope=Narrow search will be included in this table. An AE glossary table will also be produced to summarize the MedDRA coding for these events. The glossary table will include the following fields: reported term, PT, LLT, HLT, and SOC.

Furthermore, a table will be prepared to summarize injection site reactions, identified using the HLTs: "Administration site reactions NEC" and "Injection site reactions".

10.2.4.8 Hepatic events and DILI

A table for hepatic events will be created based on the SMQ of "Drug related hepatic disorders - comprehensive search (SMQ)". However, these 2 sub-SMQs are to be excluded: "Liver

neoplasms, benign (incl. cysts and polyps) (SMQ)” and “Liver neoplasms, malignant and unspecified (SMQ) “. For each of the above SMQs, include all TEAEs which code to a PT included in the Scope=Broad and/or Scope=Narrow.

Note that all AEs meeting the above criteria are to be included. It should not be limited to events that the investigator determined to be related to study drug.

Potential cases of Hy’s Law will be reported separately in a liver function test table ([Section 10.3](#)).

10.2.4.9 Summary table and figure

The incidence of the below safety topics of interest occurring during the Double-Blind Treatment Period will be reported in one summary table and displayed graphically.

- Serious infection (Terms included in SOC “Infections and Infestations”)
- Fungal infection
- Opportunistic infection
- Malignancy (Terms included in the SMQ “Malignant tumours (SMQ)”)
- Adjudicated major adverse cardiac events (MACE)
- Neutropenia
- Adjudicated suicidal ideation and behavior (SIB)
- Definite adjudicated IBD
- Definite or probable adjudicated IBD
- Anaphylactic reaction
- Hypersensitivity reaction
- Hepatic events and drug-induced liver injury

For each of the above categories, the summary table and the graph will include the incidence, the EAIR by treatment group and the risk difference (BKZ minus placebo) with its 95% CI.

The risk difference (RD) will be derived as follows:

$$RD = \frac{Ab}{Nb} - \frac{Ap}{Np}$$

The lower and upper CI bounds for RD will be calculated as follows:

$$RD - Z_{\alpha/2} * SE (RD), RD + Z_{\alpha/2} * SE (RD)$$

Where:

Ab / Ap = Number of subjects in the BKZ / Placebo group (Safety Set) affected by the event

Nb / Np = Number of subjects in the BKZ / Placebo group (Safety Set)

$Z_{\alpha/2}$ = Critical value from the standard normal distribution (1.96 for a 95% CI).

10.2.5 Special considerations for interim data snapshots

As two interim analyses are planned, there will be 2 interim data snapshots before the final analysis:

- One after the last subject completed Week 24 (visit 14),
- One after the last subject completed Week 52 (visit 28).

Some subjects will likely have pending safety outcome data at the time of the interim data snapshots. Despite this, safety tables for the interim data analyses will be based on all available data at the time of the snapshot.

For the Week 24 analysis, AE summary tables and listings will only include AEs with an onset date prior to Week 24.

For the Week 52 analysis, some AEs including the ones with onset date prior to Week 24 may have been updated. For this analysis, all TEAEs tables created for the Week 24 analysis will need to be rerun.

Because of the long SFU Period (140 days from last dose), subjects who have completed the SFU visit (and do not, therefore, enroll into the OLE study) may have a longer period of exposure than subjects who complete the study and roll in to the OLE study. For those subjects, exposure ends at 20 weeks after the last dose of IMP.

For a subject completing Week 52 and enrolled into the OLE study, exposure ends at Week 52 (visit 28).

This potential difference is acknowledged and is not considered to have a meaningful impact on the AE summaries. Furthermore, the exposure-adjusted AE summaries (which will be incorporated into many of the AE tables) would account for these differences with EAIRs and EAERs.

After the last subject has completed the final SFU visit, the study database will be locked, and TFLs will be re-run including all subjects.

10.2.6 COVID-19 impact

To assess the impact of the COVID-19 pandemic on safety, additional summaries and listings will be presented.

For reporting purposes, AEs will be assigned to either Pre-COVID-19, COVID-19, or post-COVID-19 pandemic period by comparing the AE start date (based on imputed date) to the COVID-19 pandemic period dates (AE allocated to a period if it starts during the period).

The following categories of TEAEs will be summarized by MedDRA SOC, HLT and PT, including EAIR and EAER:

- All TEAEs by time of onset relative to COVID-19 pandemic period (pre – during – post) by region and overall

- All TEAEs leading to study discontinuation and/or permanent withdrawal of study medication by time of onset relative to COVID-19 pandemic period (pre – during – post) by region and overall
- All Serious TEAEs by time of onset relative to COVID-19 pandemic period (pre – during – post) by region and overall
- All COVID-19 related TEAEs by treatment group, separately for the DBP, ATP, and the AMP, by region and overall - COVID-19 related TEAEs will be identified by the 2 preferred terms “Corona virus infection” and “coronavirus test positive” and will include confirmed or suspected COVID-19 infections.

A listing of COVID-19 related AEs will be presented where these AEs are identified as described above. Additionally, the listing of AEs will include a column for COVID-19 relatedness and the time of onset of each AE relative to the COVID-19 pandemic will be included in all AE listings.

For the purpose of calculating EAIR and EAER by COVID-19 pandemic period, the calculation of exposure time at risk presented in [Section 10.1.5](#) will be used. An individual subject may therefore be counted in the denominator for several COVID-19 pandemic periods dependent on whether the subject is still considered at risk on the COVID-19 pandemic start and stop dates. In this case time at risk will be calculated separately for each period.

10.3 Clinical laboratory evaluations

The routine clinical laboratory evaluations specified below will be evaluated:

Table 10–2: Laboratory measurements

Hematology	Biochemistry	Urinalysis
Basophils	Calcium	pH
Eosinophils	Chloride	Albumin (protein)
Lymphocytes	Magnesium	Glucose
Monocytes	Potassium	Blood
Neutrophils	Sodium	Leukocyte esterase
Hematocrit	Glucose	Nitrite
Hemoglobin	BUN	Urine dipstick for pregnancy testing ^b
MCH	Creatinine	Urine drug screen ^c
MCHC	hs-CRP	
MCV	AST	
Platelet count	ALT	
RBC count	GGT	
WBC count	ALP	

Hematology	Biochemistry	Urinalysis
	Total bilirubin	
	Triglycerides ^a	
	Cholesterol ^a	
	HDL cholesterol ^a	
	LDL cholesterol ^a	
	LDH	
	Serum pregnancy testing ^b	

ALP=alkaline phosphatase; ALT=alanine aminotransferase; AST=aspartate aminotransferase; BUN=blood urea nitrogen; ET=early termination; GGT=gamma-glutamyl transferase; HDL=high density lipoprotein; hs-CRP=high sensitivity C-reactive protein; IMP=investigational medicinal product; IMS=International Menopause Society; LDH=lactate dehydrogenase; LDL=low density lipoprotein; MCH=mean corpuscular hemoglobin; MCHC=mean corpuscular hemoglobin concentration; MCV=mean corpuscular volume; RBC=red blood cell; SFU=Safety Follow-up; WBC=white blood cell

^a Biochemistry will include triglycerides, cholesterol, HDL cholesterol, and LDL cholesterol at Baseline, Weeks 12 and 24, and at the ET visit.

^b Pregnancy testing will consist of serum testing at the Screening visit for all women of childbearing potential. The pregnancy test will be urine at all other visits.

^c Urine drug screen will be performed at Screening visit.

Biochemistry and hematology values will be flagged based on their reference range:

- Values that are below the lower limit of the reference range will be flagged as 'L' (low)
- Values that are above the upper limit of the reference range will be flagged as 'H' (high)
- All other values will be referenced as normal.

Markedly abnormal values for blood chemistry and hematology will be defined as laboratory values graded 3 or 4 according to the Rheumatology Common Toxicity Criteria (RCTC). Definitions of the markedly abnormal values are given in [Table 10-3](#) and [Table 10-4](#) and are based on the RCTC units. All units in the tables below will be converted to the standard units based on Clinical Data Interchange Standards Consortium (CDISC) standards.

Table 10-3: Definitions of markedly abnormal biochemistry values

Parameter name	Unit	Criteria	Abnormal designation
Creatinine	mmol/L	>3.0 x ULN or >3.0 x Baseline	AH
Glucose	mmol/L	<2.2 >13.9	AL AH
Calcium	mmol/L	>3.1 <1.75	AH AL
Magnesium	mmol/L	>1.23 <0.4	AH AL

Parameter name	Unit	Criteria	Abnormal designation
Potassium	mmol/L	>6.0	AH
		<3.0	AL
Sodium	mmol/L	>155	AH
		<130	AL
Triglyceride	mmol/L	>5.7	AH
Cholesterol	mmol/L	>10.34	AH

AH=abnormal high; AL=abnormal low; dL = deciliter; L = liter; mg = milligram; mmol = millimoles; ULN = upper limit of normal.

Table 10–4: Definitions of markedly abnormal hematology values

Parameter name	Unit	Criteria	Abnormal designation
Hemoglobin	g/L	<80	AL
		>40 above ULN or >40 above Baseline if Baseline is above ULN	AH
Lymphocytes Absolute	$10^9/L$	<0.5	AL
		>20.0	AH
Neutrophils Absolute	$10^9/L$	<1.0	AL
Platelets	$10^9/L$	<50	AL
WBC/ Leukocytes	$10^9/L$	<2.0	AL
		>100	AH

Table 10–5: Definitions of markedly abnormal liver enzyme elevation values

Parameter name	Unit	Criteria	Abnormal designation
Alkaline Phosphatase		>5.0 x ULN	AH
ALT	U/L	>5.0 x ULN	AH
AST	U/L	>5.0 x ULN	AH
Total Bilirubin	umol/L	>3.0 x ULN	AH
GGT	U/L	>5.0 x ULN	AH

ALT= alanine aminotransferase; AST = aspartate aminotransferase; GGT= gamma-glutamyltransferase

Definitions of the markedly abnormal values for liver enzyme elevation are given in [Table 10–5](#).

All laboratory summaries will be presented in standard international (SI) units and will be based on observed case values. In the case where laboratory values are below the LLOQ, then these will be set to the midpoint between 0 and the LLOQ for the purpose of summarizing the data.

In the case where laboratory data are expressed as above a fixed value (ie, “>xx.xx”), then the numeric portion of the value will be used (ie, xx.xx) to present and calculate statistics.

To define the minimum/maximum post-Baseline values, all post-Baseline assessments including those at unscheduled visits (but excluding any that occur more than 140 days after the last administration of study medication) will be used.

The following additional rule will be also applied :

Subjects who have completed PA0010 and have a PA0012 start date, only PA0010 results up to and including the PA0012 start date will be used to find the subjects minimum or maximum results. Additionally, subjects who are in PA0012 without a start date (date of first dose), only PA0010 results up to the Week 52 visit + 14 days will be used to find the subjects minimum or maximum results.

Different summary tables for hematology, biochemistry variables (except hs-CRP which will be analyzed in the efficacy section) and urinalysis (pH, Albumin (protein), glucose, blood, leukocyte esterase and nitrite) will be provided in the SS. For shift tables, results for the DBP and the ATP will be presented together for the overall study period.

As indicated in [Section 3.1](#), for tables where data are summarized by visit only values occurring at scheduled visits will be included.

For each laboratory parameter, the below results will be presented for the overall study period, by treatment (Placebo/BKZ 160mg Q4W, BKZ 160mg Q4W and ADA 40mg Q2W):

- Observed values at Baseline and observed values and changes from Baseline at each scheduled post-Baseline visit
- Number and percentage of subjects by CTCAE grade (version 4.03) (when applicable) based on minimum/maximum post Baseline value (for blood chemistry and hematology). Subjects who meet the decreased potassium criterion of $3.0 < \text{LLN}$, which is specified as the decreased potassium lab criterion for both CTCAE Grade 1 and Grade 2, will be counted as Grade 2.
- Shift in CTCAE grade from Baseline to minimum/maximum post-Baseline value (for blood chemistry and hematology)
- Number and percentage of subjects meeting the below criteria at any time during the study:
 - AST: $>2 \times \text{ULN}$, $>3 \times \text{ULN}$, $>5 \times \text{ULN}$, $>10 \times \text{ULN}$, $>20 \times \text{ULN}$
 - ALT: $>2 \times \text{ULN}$, $>3 \times \text{ULN}$, $>5 \times \text{ULN}$, $>10 \times \text{ULN}$, $>20 \times \text{ULN}$
 - AST or ALT: $>2 \times \text{ULN}$, $>3 \times \text{ULN}$, $>5 \times \text{ULN}$, $>10 \times \text{ULN}$, $>20 \times \text{ULN}$
 - Bilirubin: $>1 \times \text{ULN}$, $>1.5 \times \text{ULN}$
 - ALP: $>2 \times \text{ULN}$
- Number and percentage of subjects with potential Hy's Law cases based on the 2 following definitions:
 - $[\text{AST} \geq 3 \times \text{ULN} \text{ or } \text{ALT} \geq 3 \times \text{ULN}] \text{ and Total Bilirubin} \geq 2 \times \text{ULN}$
 - $[\text{AST} \geq 3 \times \text{ULN} \text{ or } \text{ALT} \geq 3 \times \text{ULN}] \text{ and Total Bilirubin} \geq 2 \times \text{ULN}$ in the absence of $\text{ALP} \geq 2 \times \text{ULN}$

To meet either of the above criteria, a subject must experience the elevation in bilirubin and ALT or AST (and the absence of ALP elevation, if applicable) at the same visit.

The below results will be presented on the SS (for the DBP), on the ATS (for the ATP by treatment and for all BKZ-treated subjects), and on the AMS (for all the BKZ-treated subjects and on the ADA group). All values observed at any time while on treatment (ie, occurring at scheduled and unscheduled visits) will be included in the below tables. Baseline values and values observed more than 140 days after the last administration of study medication are not considered:

- Number and percentage of subjects with treatment-emergent markedly abnormal laboratory data overall (for blood chemistry and hematology), All values observed at any time while on treatment (ie, occurring at scheduled and unscheduled visits) will be included in this table summarizing markedly abnormal values. For this summary, Baseline values and values observed more than 140 days after the last administration of study medication are not considered.
- Number and percentage of subjects with markedly abnormal liver enzyme elevation tests (data beyond the CTCAE Grade 3 thresholds as outlined in [Table 10-5](#))

All laboratory data will be listed by treatment, subject and visit including changes from Baseline for numeric variables, flags for measurements outside the normal ranges, the relative study day, a flag for whether the test was not done and a flag for whether the subject was fasting.

The markedly abnormal laboratory data will also be listed separately.

Listings will also include Hepatitis B and C, human immunodeficiency virus (HIV), genomic proteomic/metabolomics, and genetic/epigenetic tests.

In addition, the laboratory results classified as Grade 3 or Grade 4 will be listed separately.

Urinalysis laboratory results and hepatic events will be listed separately.

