2.3 Study design and conduct

2.3.1 Study description

This is a Phase 3, multicenter, randomized, double-blind, placebo-controlled, noninferiority active reference study to evaluate the efficacy and safety of BKZ in subjects with active PsA who are biologic disease-modifying antirheumatic drug (bDMARD) naive. To be eligible to participate in this study, subjects must be adults with a diagnosis of active PsA based on the Classification Criteria for Psoriatic Arthritis (CASPAR) and have disease with TJC ≥ 3 and SJC ≥ 3 . In addition, subjects should not have been previously exposed to any bDMARD for PsA or PSO to be eligible for the study.

Approximately 840 subjects will be randomly assigned in a 3:2:1 ratio, stratified by region (North America, Western Europe, Eastern Europe, and Asia/Australia) and bone erosion (0, ≥ 1) to 1 of the 3 following blinded treatment groups:

- Bimekizumab 160mg sc Q4W (420 subjects),
- Placebo (280 subjects),
- Adalimumab sc 40mg every 2 weeks (Q2W) (140 subjects).

It is planned to enroll a minimum of 45% of subjects who have elevated hs-CRP (≥ 6 mg/L) and/or who have at least 1 bone erosion at Screening.

[figure not shown]
The overall study design consists of:

- a Screening Period (≥ 14 days to ≤ 35 days)
- a 16-week placebo controlled Double-Blind Treatment Period (DBP)
- a 36-week Active Treatment-Blind Period (ATP) (Week 16 to week 52)
- a Safety Follow Up (SFU) visit, 20 weeks after the final dose of IMP (for subjects not entering the open label extension (OLE) study or who discontinue early, including those withdrawn from IMP, as applicable).

The maximum study duration per subject will be up to 73 weeks.

The study schematic diagram for the study is presented in.

Figure 2-1: Study schematic diagram

ACR50=American College of Rheumatology 50% response criteria, BKZ=bimekizumab, PsA=psoriatic arthritis; Q2W=every 2 weeks, Q4W=every 4 weeks, sc=subcutaneous, SFU=Safety Follow-Up, W=week

^a Adalimumab dosing is performed every 2 weeks from Baseline to Week 50.

^b After 16 weeks of double-blind treatment, subjects will enter the Active Treatment-Blind Period. All subjects randomized to placebo will be reallocated to receive BKZ 160mg Q4W. Subjects randomized to BKZ 160mg Q4W will continue to receive their originally randomized dose. Subjects randomized to active reference (ADA) will continue with their active treatment.

^c Permitted rescue therapy is defined in Protocol Section 5.4.

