2.3.2.3 Active Treatment-Blind Period

After the 16-week DBP, subjects will enter the 36-week ATP. At Week 16 (Visit 10), subjects will be allocated to treatment regimens as follows:

- Subjects in the BKZ 160mg sc Q4W group will continue to receive BKZ 160mg sc Q4W
- Subjects in the placebo group will be reallocated to BKZ 160mg sc Q4W Subjects in the ADA 40mg sc Q2W group will continue to receive ADA 40mg sc Q2W.

As for the DBP, BKZ and ADA will be administered sc by unblinded study personnel at the clinical site. The first dose in the ATP will be administered at Week 16 after all assessments have been completed.

During the 36 weeks of the ATP, IMP administration will be performed every 2 weeks (allowed visit window between 11 and 17 days) at Study visits (from Visit 10 – Week 16 through Visit 27 - Week 50).

Visit 28 (Week 52) ends the ATP, and the last assessments for that period are collected during that visit.

Subjects who withdraw early from the study will undergo the ET visit assessments and will enter the SFU Period, as applicable. Subjects who withdraw from IMP during the ATP will be encouraged to return for all remaining scheduled visits up to Week 52 and the SFU visit (20 weeks after their final dose of IMP).

At the completion of the ATP, investigators should discuss treatment options with the subject. Subjects who complete PA0010 (ie who performed all visits up to Week 52 and not having permanently discontinued IMP and who did not meet any of the withdrawal criteria) will be given the opportunity to enter the OLE study at Week 52.

The ATP starts on the day of dose administration at Week 16 and ends at Week 52 (Visit 28) or at the Early Termination visit (ET Visit) for subjects withdrawn from the study after Week 16 and before Week 52. This period should last 36 weeks maximum.

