ACR= American College of Rheumatology, ADA=Adalimumab, AE=adverse events, ATP=Active Treatment-Blind Period, ATS=Active Treatment-Blind Set, AMP=Active Medication Periods, AMS=Active Medication Set, BKZ=Bimekizumab, DBP=Double-Blind Treatment Period, eC-SSRS=electronic Columbia Suicide Severity Rating Scale, ECG=electrocardiogram, FAS=Full Analysis Set, PASI= Psoriasis Area and Severity Index, RS=Randomized Set, SS=Safety Set

*For subjects in the Radiographic Set for vdHmTSS

Note: Subjects in the Placebo/ BKZ 160mg Q4W treatment group are taking BKZ 160 mg Q4W treatment after Week 16.

- The final analysis.

The final analysis will consist of a rerun of all analyses provided during the preceding Week 52 analysis. This includes new SFU data that were not available for the Week 52 analysis. If there is no SFU data ongoing, the final analysis will be identical to the Week 52 analysis.

Prior to the final analysis, additional data cuts may be prepared following regulatory requests or for publication purposes.

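### The liver-threshold, potential Hy's Law and CTCAE-grade tables have no version for the 16-week placebo-controlled period

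*SAP*

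**What the plan says.** SAP Section 10.3 (Clinical laboratory evaluations) gives two lists of laboratory outputs with different reporting periods.

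**First list, overall study only.** Its lead-in is "the below results will be presented for the overall study period, by treatment (Placebo/BKZ 160mg Q4W, BKZ 160mg Q4W and ADA 40mg Q2W"). Under it stand:
- observed values and changes by visit;
- subjects by worst CTCAE grade;
- shifts in CTCAE grade;
- threshold counts: AST and ALT from >2x to >20x ULN, bilirubin >1x and >1.5x ULN, ALP >2x ULN;
- two definitions of a potential Hy's Law case, both needing AST or ALT at 3x ULN or more with total bilirubin at 2x ULN or more at the same visit.

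The threshold counts are introduced as "Number and percentage of subjects meeting the below criteria at any time during the study". The same section adds: "For shift tables, results for the DBP and the ATP will be presented together for the overall study period". Table 4-4 likewise assigns the by-visit and shift laboratory tables to the overall study period.

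**Second list, split by period.** It begins "The below results will be presented on the SS (for the DBP), on the ATS" and continues to the AMS. It holds only treatment-emergent markedly abnormal values and markedly abnormal liver tests. Table 10-5 sets the latter at >5x ULN for ALT, AST, ALP and GGT and >3x ULN for total bilirubin.

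Section 2.3.1 describes "a 16-week placebo controlled Double-Blind Treatment Period (DBP") followed by "a 36-week Active Treatment-Blind Period (ATP) (Week 16 to week 52"). Section 2.3.2.3 states: "Subjects in the placebo group will be reallocated to BKZ 160mg sc Q4W". The note to Table 4-4 confirms the column label: "Subjects in the Placebo/ BKZ 160mg Q4W treatment group are taking BKZ 160 mg Q4W treatment after Week 16".

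Section 10.2.4.8 sends potential Hy's Law cases to the liver function table of Section 10.3, which is in the unsplit list.

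**The concern.** Hepatic events and DILI are a named safety topic. At the lower enzyme thresholds and for the combined transaminase-bilirubin signal, the only planned summary sets BKZ beside a column that is itself on BKZ for most of the study. A placebo subject whose ALT first exceeds 3x ULN at Week 30, on BKZ, is counted in the Placebo/BKZ column exactly like one whose elevation occurred at Week 8 on placebo. A true BKZ excess is therefore pulled toward no difference in ratio terms, and the table cannot show which treatment preceded the elevation.

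This also departs from the SAP's own practice. TEAEs, the safety topics of interest, markedly abnormal laboratory values and markedly abnormal blood pressure are all produced for the DBP on the SS, the ATP on the ATS and the AMP on the AMS. No reason is given for treating the liver thresholds and Hy's Law differently. These tables also lack the all-BKZ column that the ATS and AMS outputs carry.

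**Working it through.** **1. Time on BKZ in the Placebo/BKZ column.** Section 2.3.1 gives 16 weeks of DBP and 36 weeks of ATP: 16 + 36 = 52 weeks. The share on BKZ is 36/52 = 69.2%. Follow-up after Week 52 is ignored.

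**2. Which liver outputs have a DBP version.**

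| Output | DBP version planned? | Where |
|---|---|---|
| ALT/AST/ALP/GGT >5x ULN, bilirubin >3x ULN | Yes, on the SS | Section 10.3 second list; Tables 10-5 and 4-4 |
| Hepatic TEAEs | Yes, with a BKZ-minus-placebo risk difference and 95% CI | Sections 10.2.4, 10.2.4.8 and 10.2.4.9 |
| Values and changes by visit | In effect yes, through Week 16 | Section 10.3 first list |
| AST/ALT >2x and >3x ULN | No | Section 10.3 first list |
| Bilirubin >1x and >1.5x ULN; ALP >2x ULN | No | Section 10.3 first list |
| Potential Hy's Law, both definitions | No | Section 10.3 first list; Section 10.2.4.8 |
| Worst CTCAE grade and grade shift | No | Section 10.3 first list; Table 4-4 for shifts |

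**3. A case that falls through.** Take a subject with ALT 4x ULN and total bilirubin 2.5x ULN at one DBP visit. Since 4 ≥ 3 and 2.5 ≥ 2, the subject meets the first Hy's Law definition. Since 4 < 5 and 2.5 < 3, the subject meets neither Table 10-5 cut-off. No DBP laboratory abnormality table counts this subject. A DBP hepatic TEAE table would do so only if the finding were reported as an adverse event.

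**4. Rough size of the dilution.** The SAP gives no liver event rates, so this is an illustration. Assume a constant hazard on each treatment, full follow-up to Week 52 and a true BKZ:placebo rate ratio R. Expected events are proportional to 52R in the BKZ column and to 16 + 36R in the Placebo/BKZ column:

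apparent ratio = 52R / (16 + 36R)

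- R = 1.5: 78/70 = 1.11
- R = 2: 104/88 = 1.18
- R = 3: 156/124 = 1.26

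**5. The same check counting subjects, as the tables do.** With 16-week risks p_P (placebo) and p_B (BKZ), the 52-week risks are:
- BKZ column: 1 − (1 − p_B)^(52/16)
- Placebo/BKZ column: 1 − (1 − p_P)(1 − p_B)^(36/16)

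For assumed p_P = 1% and p_B = 2%, these are 6.35% and 5.40%, a ratio of 1.18. The difference is 0.96 points against 1.0 point in the DBP. Across assumed placebo risks of 0.5% to 2%, true 16-week risk ratios of 1.5 to 5 all appear as about 1.11 to 1.31.

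**6. Week 24 analysis.** Safety tables run to the cut-off date, the last subject's Week 24 visit. If every subject stopped exactly at Week 24, R = 2 would appear as 2×24/(16 + 2×8) = 48/32 = 1.5. Subjects enrolled earlier contribute more BKZ time, so the dilution would be greater than that.

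**The case against.** The strongest reply is that the placebo-controlled liver evaluation is largely intact. The higher single-parameter elevations have a DBP table. Hepatic TEAEs, from a comprehensive search that does not depend on investigator causality, have DBP tables and a risk difference with a confidence interval. By-visit values to Week 16 are unconfounded. This stands. A reader might infer from Section 10.3 that the placebo-controlled liver comparison as a whole is diluted away; the documents do not support that.

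A reader might also infer that placebo-period and BKZ-period elevations cannot be told apart. That is true only within the summary tables. All laboratory data are listed by subject and visit with relative study day (Section 10.3), and Section 3.2.1 adds a second relative day, counted from the first BKZ injection, for switched placebo subjects in safety listings. Individual cases can be dated, and if Hy's Law cases are very few the listings may suffice.

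Three further points are fair. The comparison with ADA in the overall tables is not affected by switching, because that arm continues its treatment. The tables are descriptive, with no planned test or ratio, so no hypothesis or error rate is touched. The dilution figures rest on assumptions, and for small effects the absolute difference hardly moves.

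What remains is that no planned summary gives the randomised comparison below the Table 10-5 cut-offs or for the combined Hy's Law criterion. Listings permit reconstruction but do not replace a count by arm.

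**Conclusion.** The point holds in this limited form. The AST/ALT, bilirubin and ALP threshold counts, both potential Hy's Law definitions and the worst-CTCAE-grade and shift tables are planned only for the overall study, with a Placebo/BKZ column on BKZ for 69.2% of the 52 weeks. The DBP comparison is missing for transaminases >2x and >3x ULN, bilirubin >1x and >1.5x ULN, ALP >2x ULN, Hy's Law and the CTCAE grades and shifts.

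The 36 of 52 weeks and the missing DBP versions follow directly from the SAP. The ratios of 1.11, 1.18 and 1.26 for true ratios of 1.5, 2 and 3 show direction and rough size only; they depend on a constant hazard, full follow-up and rates that the SAP does not give. The primary efficacy conclusion is not affected. This is an inexpensive improvement on a named safety topic, and it should be made.

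**What to change.** - In Section 10.3, add the liver threshold counts, both Hy's Law definitions and the worst-CTCAE-grade and shift tables to the list produced for the DBP on the SS (Placebo, BKZ, ADA), the ATP on the ATS and the AMP on the AMS.
- Amend the sentence in Section 10.3 that presents shift results for the DBP and ATP together.
- Amend the Table 4-4 row for shift tables to match, and add the liver threshold and Hy's Law tables there with the same three periods.
- Keep the overall-study versions as a supplement.

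The cost is SAP wording and a few additional table runs. The data, periods and analysis sets already exist. The AMS and ATS versions would also supply the all-BKZ column that these tables now lack.
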